12.9.6.2 Pregnancy

Subjects will be counseled to inform the investigator of any pregnancy that occurs during study treatment and for 90 days after the last dose of study drug.

If a subject or the female partner of a male subject becomes pregnant while participating in the study, study treatment must be permanently discontinued immediately. The investigator must notify the medical monitor and Vertex Global Patient Safety within 1 business day of the site's knowledge of the subject's (or partner's) pregnancy, by utilizing the Initial Pregnancy Notification Report Form.

If confirmed to be on active drug, the subject or partner will be followed until end of pregnancy and the infant will be followed for 1 year after the birth, provided informed consent is obtained from at least 1 parent. A separate informed consent form will be provided to explain these follow-up activities. Pregnancy itself does not constitute an adverse event.

13 STATISTICAL AND ANALYTICAL PLANS

Analysis of all data, including safety, PK profiles, efficacy, and synovial biopsies will be performed by Vertex or designee. The results of all parts of the study will be reported in the clinical study report. A detailed analysis plan for the analysis of safety data and efficacy data will be presented in a statistical analysis plan (SAP), and a detailed analysis plan for PK profiles will be presented in a clinical pharmacology analysis plan (CPAP) before the database is locked for analysis.

As synovial biopsy subjects will only be randomized to the 200 mg qd VX-509 dose (Arm C), potential bias is introduced related to patient selection, subjective assessments, and other subject interactions. To minimize the impact of this potential bias, subjects in the Synovial Biopsy Subset will know that they are not receiving placebo, but not the VX-509 dose they are receiving. Centrally blinded MRI reading limits the potential impact on RAMRIS scores.

13.1 Sample Size and Power

Due to the small sample size of this trial, the study is not powered for demonstration of the significant changes in the treatment arm(s) as compared to placebo. Assuming that the true ACR20-CRP rates at Week 12 are 25%, 38%, 60%, and 65% for the 4 treatment groups, respectively (placebo, 100 mg, 200 mg, and 300 mg VX-509 qd), the study has approximately 25% power to demonstrate a significant difference between placebo and the 300 mg (highest) VX-509 dose.

The study will be utilized to evaluate early effects on the level of synovitis and bone marrow edema (osteitis) by MRI, and the dose-ranging information on RAMRIS scores will be utilized at end of Phase 2 to select the pivotal VX-509 dose(s) for study in Phase 3 clinical studies.

A published 24 week study evaluating golimumab 100 mg with or without concurrent methotrexate (MTX) in early RA subjects who were MTX-naïve showed mean baseline (interquartile range; minimum and maximum from any arm) RAMRIS scores of 8.8 to 10.3 (4.0 to 14.5), 8.4 to 11.5 (1.5 to 17.8), and 17.7 to 25 (8.8 to 27.0) for synovitis, bone marrow edema, and erosion, respectively. Mean (standard deviation [SD]) change from baseline in placebo arm RAMRIS scores (N = \sim 60) were 0.14 (2.98), 0.56 (3.97), and 0.24 (3.38) for synovitis, bone marrow edema, and erosion, respectively. Changes from baseline for subjects receiving golimumab 100 mg therapy alone (N = \sim 60) were -1.76 (2.76), -2.04 (5.69), and 0.51 (3.09) for synovitis, bone marrow edema, and erosion, respectively. Changes from baseline for subjects receiving golimumab 100 mg therapy with MTX (N = \sim 62) were -2.18 (3.26), -1.22 (4.88), and 0.00 (0.83) for synovitis, bone marrow edema, and erosion, respectively. Using the golimumab + MTX scores, a trial would be 80% powered with 30, 100, and 1650 subjects per arm for synovitis, bone marrow edema, and erosion RAMRIS scores, respectively.

13.2 Analysis Sets

The Randomized Set is defined as all subjects who received a subject ID number and randomization with treatment assignment from the IVRS/IWRS.

The Full Analysis Set (FAS) is defined as all randomized subjects who received at least 1 dose of study drug. The FAS is an intention-to-treat efficacy analyses set in which subjects will be analyzed according to their randomized treatment group.

The Safety Set is defined as all randomized subjects who received at least 1 dose of study drug. The Safety Set is to be used for all safety analyses in which subjects will be analyzed according to the actual treatment they received on Day 1.

The MRI Set is defined as all subjects in the FAS Set who had at least 1 post-baseline MRI assessment.

The PK Set is defined as all subjects in the Safety Set who had at least 1 post-baseline PK sample assessment.

The Synovial Biopsy Subset is defined as all patients in the Safety Set who had at least 1 post-baseline synovial biopsy performed.

13.3 Statistical Analysis

The Vertex Biometrics Department or its designee will analyze the efficacy, safety, and tolerability data. Methodological and related details will be provided in the SAP for this study, which will be finalized before clinical database lock.

13.3.1 General Considerations

Continuous data will be summarized by treatment group using the following descriptive summary statistics: the number of subjects (n), mean, standard deviation (SD), median, minimum value (min), and maximum value (max). For each continuous variable, if the measurements in the eCRF data are integers, then the corresponding mean and median will be presented to 1 decimal place and the SD to 2 decimal places; if the measurements are obtained to 1 decimal place, then the mean and median will be presented to 2 decimal places and the SD to 3 decimal places and so forth. Minimum and maximum will be displayed as reported in the eCRF data.

Categorical variables will be summarized using counts and percentages. Percentages will be presented to 1 decimal place unless otherwise specified.

Summaries of continuous and categorical data will be presented, as appropriate, by treatment group, for all treatment groups combined, and scheduled time points. The scheduled time points are presented in the assessment schedule in Table 3-1 and Table 3-2.

All subject data, including those derived, will be presented in the subject data listings; listings will display all subjects who were enrolled, regardless of whether or not they received study drug.

Unscheduled Visits: If a subject's unscheduled visit falls within the allowed visit window, then the unscheduled assessment will be subject to selection methods defined under the visit windows. All other unscheduled assessments will be included in subject data listings only.

Data handling conventions: For visit level summaries, the visit windows will be used to identify observations to be included in each visit summary.

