12.9.5 Electrocardiograms

Standard 12-lead Electrocardiograms (ECGs) will be performed using a machine with printout at the time points indicated in Table 3-1 and Table 3-2.

Additional 12-lead ECGs should be performed at any other time if clinically indicated.

The performance of all ECGs must adhere to the following guidelines:

- The subject will be instructed to rest in the supine position for at least 5 minutes before having an ECG performed.
- The ECG will be performed before any other procedures that may affect heart rate (e.g., blood draws).

The ECG traces will be manually read at the site at the Screening and Follow up Visits. The ECG machine will compute the PR, QT, and QTc intervals, QRS duration, and heart rate. RR intervals may be computed on site, or calculated later during analysis if this function is not available on site. A printout of the ECG traces will be made for safety review by the investigator and maintained with source documentation. Any clinically significant ECG abnormalities at screening will exclude the subject's participation in the study. Clinically significant ECG abnormalities occurring during the study through the Safety Follow-up Visit will be recorded as AEs.

To ensure safety of the subjects, a qualified individual at the investigator site will make comparisons to baseline measurements. If the QTc is increased by >45 msec from the baseline or an absolute QTc value is ≥500 msec for any scheduled ECG, 2 additional ECGs will be performed approximately 2 to 4 minutes apart to confirm the original measurement. If either of the QTc values from these repeated ECGs remains above the threshold value (>45 msec from baseline or ≥500 msec), a single ECG must be repeated at least hourly until QTc values from 2 successive ECGs fall below the threshold value that triggered the repeat measurement.

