13.3.4.3 Electrocardiograms

A summary of raw values and change from baseline values will be provided by treatment group at each scheduled visit for the following ECG measurements: PR, QT, QRS, and QTc intervals and heart rate. In addition, the number and percentage of subjects by maximum on-treatment value of QT/QTc intervals, categorized as \leq 450 msec, \geq 450 msec and \leq 480 msec, \geq 480 msec and \leq 500 msec, and \geq 500 msec, as well as maximum on-treatment change from baseline value of QT/QTc intervals, categorized as \leq 30 msec, \geq 30 msec and \leq 60 msec, and \geq 60 msec. A listing of subjects with abnormal, clinically significant ECGs will also be provided.

13.3.4.4 **Vital Signs**

The following vital signs will be summarized by treatment group at each scheduled time point: systolic and diastolic blood pressure (mmHg), body temperature, pulse rate (beats per minute [bpm]), and respiratory rate (breaths per minute). Clinically significant abnormal findings in vital signs will be reported as adverse events.

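### As worded, the listings-only rule in Protocol 13.3.1 keeps between-visit ECGs out of the maximum on-treatment QT/QTc categories in 13.3.4.3

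*Protocol*

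**What the plan says.** Protocol Section 13.3.1 sorts unscheduled assessments into two groups. Those inside a visit window go through the selection method for that window. For the rest: "All other unscheduled assessments will be included in subject data listings only". The next paragraph of the section gives the purpose of the windows: "For visit level summaries, the visit windows will be used to identify observations to be included in each visit summary".

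Section 13.3.4.3 first asks for ECG values and changes at each scheduled visit. It then asks, as an addition, for numbers and percentages of subjects by "maximum on-treatment value of QT/QTc intervals" (cut points 450, 480 and 500 msec) and by "maximum on-treatment change from baseline value of QT/QTc intervals" (cut points 30 and 60 msec). Neither count is tied to a visit.

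Section 12.9.5 provides for ECGs off the schedule: "Additional 12-lead ECGs should be performed at any other time if clinically indicated".

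Table 3-2 schedules 12-lead ECGs on Day 1 (labelled baseline), at Week 6, and at Week 12 or early termination.

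**The concern.** A maximum on-treatment value is meant to catch the worst reading a subject had while taking the drug. An ECG done between visits because something worried the investigator is a likely place to find that reading. The rule in 13.3.1, followed as written, removes it from every table, including the one table designed to show extremes.

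At stake is whether the QT/QTc category table describes each subject's true on-treatment maximum or only the maximum over a small set of windowed records. The omission can act in one direction only, towards a lower category.

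**Working it through.** No figure in the protocol needs reproducing. The check is a comparison of the rules, a direction argument and one small calculation.

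**1. Does any ECG meet both rules?** Take an ECG done during dosing, for a clinical reason, outside every visit window.

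| Provision | Treatment of that ECG |
|---|---|
| 12.9.5 | Should be performed |
| 13.3.4.3 | Is an on-treatment value, so belongs in a per-subject on-treatment maximum |
| 13.3.1 | Listing only |

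The second and third rows cannot both be followed if 13.3.1 means what it says.

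**2. Is there a written exception?** The restriction to visit-level summaries stands in the following paragraph of 13.3.1. It governs how windows are used and is not attached to the listings-only sentence. Section 13.3.4.3 does not say which ECG records feed the maximum.

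**3. What remains if the ECG is dropped?** Section 13.3.4 defines the safety baseline as the last non-missing value before the first dose, and I assume the Day 1 ECG is taken before that dose. A subject who completes treatment then has two scheduled post-baseline ECGs, at Weeks 6 and 12. Any unscheduled ECG that a window's selection method keeps would add to these.

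**4. Direction.** Let S be the retained ECGs and A all on-treatment ECGs, with S contained in A. Then max(S) ≤ max(A). Because a subject's baseline is fixed, max(S) − baseline ≤ max(A) − baseline. Dropping records can lower a category or leave it unchanged, and can never raise it. For example, a subject at or below 450 msec at both Week 6 and Week 12, but above 500 msec on a between-visit ECG, would be counted in the lowest category.

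**5. Size per subject.** Section 9.1 plans 10 subjects per arm. One subject in too low a category changes that arm's percentage by 1/10 = 10.0 percentage points.

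**6. Number of subjects affected.** This cannot be computed. The protocol gives neither the analysis windows nor an expected number of unscheduled ECGs.

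**The case against.** The best defence is context. The sentence sits under a heading on unscheduled visits and completes a rule about visit windows, and the next paragraph links windows to visit-level summaries. A specific instruction for a maximum ordinarily overrides a general convention. On that reading nothing is lost, and it may well be what was intended. It can also be said that choosing the records for such a table is normal SAP detail, that a maximum over windowed ECGs is still computable, and that 13.3.4.3 never says unscheduled ECGs enter it.

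Much of this stands, and it is why the point is minor. It does not remove the point. The protocol is not silent here: it states a rule without exception, and a programmer who follows that rule builds the maximum from windowed records only. The by-visit limit has to be inferred.

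The safeguards are real. Section 13.3.1 says "All subject data, including those derived, will be presented in the subject data listings", and 13.3.4.3 says "A listing of subjects with abnormal, clinically significant ECGs will also be provided". Section 12.9.5 has clinically significant ECG abnormalities recorded as adverse events. With about 40 subjects, listings can be read in full.

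Four stronger readings might be inferred, and the documents do not support them:

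- *The threshold-triggered repeats are lost.* Section 12.9.5 says "2 additional ECGs will be performed approximately 2 to 4 minutes apart to confirm the original measurement". These follow a scheduled ECG by minutes and would normally share its window.
- *The laboratory shift tables lose off-schedule values.* That would follow only if shifts were worst post-baseline. Section 13.3.4.2 does not say so, and if shifts are by visit, nothing is lost.
- *The study drug is shown to prolong QTc.* Section 10.3 mentions prolonged QTc for co-medications whose exposure the study drug may raise, not as an effect of the study drug itself.
- *Most on-treatment ECGs would be dropped.* If analysis windows equalled the Table 3-2 tolerances and Week n were Day 7n+1, the ECG windows would cover 7 + 7 = 14 of 84 dosing days, leaving 70 (83%) outside. Adding the Week 2 and Week 8 windows (7 + 15 days) leaves 48 (57%). Contiguous windows leave 0. The range reflects an undefined window and counts calendar days, not ECGs or subjects, so it is no measure of effect.

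**Conclusion.** The point holds on the wording. Section 13.3.1, read as written, excludes clinically indicated between-visit ECGs from the maximum on-treatment QT/QTc value and change categories in 13.3.4.3, and this could understate a subject's category. Severity is minor. The effect is limited to a descriptive safety table and needs a subject whose highest QT/QTc falls on an out-of-window unscheduled ECG and lies in a higher category than the retained values. No efficacy analysis is affected.

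The conclusion rests on the literal reading of 13.3.1, on the Day 1 ECG being pre-dose, and on visit windows that do not cover the whole treatment period. If the SAP sets contiguous windows, the listings-only rule no longer applies during treatment, and the selection method within each window decides whether the highest value is kept. The SAP is not at hand and may already settle the matter.

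**What to change.** Make two edits, in the protocol or the SAP:

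- In 13.3.1, limit the listings-only sentence to by-visit summaries.
- In 13.3.4.3, state that the maximum QT/QTc value and change categories use all scheduled and unscheduled on-treatment ECGs. This also covers in-window ECGs that a selection method would otherwise pass over.

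The cost is one sentence in each place, and 13.3.1 already has all subject data listed. The small downside is that subjects who are monitored more closely contribute more values to the maximum. No new laboratory table is needed on this account.

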13.3.2 Background Characteristics

13.3.2.1 Subject Sets

Subject numbers will be summarized by study arm, showing the number and percentage of subjects in the following defined subject sets, as appropriate: Randomized Set, FAS, Safety Set, MRI Set, PK Set and Synovial Biopsy Set.

13.3.2.2 Subject Disposition

Subject disposition data will be summarized for the FAS and Safety set (if different from the FAS), showing the number and percentage of subjects in the following categories, as appropriate:

- Completed 12 weeks of dosing
- Prematurely discontinued dosing and the reasons for discontinuation

- Completed the Safety Follow-up Visit
- Prematurely discontinued the study between end-of-dosing and the Safety Follow-up Visit and the reasons for discontinuation

13.3.2.3 Demographics and Baseline Characteristics

Demographic and baseline characteristics will be summarized by FAS. Demographics will include age, gender, race, weight, height, BMI, region (United States, Other). Baseline characteristics will include duration of RA, DAS28-4(CRP), tender joint count, swollen joint count, CRP, ESR, rheumatoid factor (RF) (negative/positive), anti-CCP antibody status (negative/positive), RF and CCP status (RF+/CCP+, RF+/CCP-, RF-/CCP+, RF-/CCP-), current smoking status, HAQ-DI, subject assessment of pain, subject global assessment, physician global assessment, prior biologic response modifier (including anti-TNF) use (yes/No), previous number of DMARDs used (biologic + nonbiologic), baseline erosion status (yes/No), baseline vdHmTSS, and baseline RAMRIS scores (synovitis score, bone marrow edema (osteitis), erosion score, joint space narrowing score).

Continuous variables will be summarized by descriptive summary statistics and categorical variables will be summarized by counts in each category. For the RF and CCP status summary, if there is missing information, it will be considered as negative status. Duration of RA is defined as number of months between date of RA diagnosis and date of randomization. If day of diagnosis is missing, 15th day of the month will be used for duration calculation. If month is missing, July 1st of the diagnosis year will be imputed for the duration calculation.

Medical history will be presented in a subject data listing for condition/diagnosis and each medical history condition will be recorded as ongoing or not on the date of informed consent.

No statistical tests will be carried out to evaluate any baseline imbalance between dose groups.

13.3.2.4 Tuberculosis Screening

A PPD skin test and a serum QuantiFERON assay will be conducted at Screening to test for tuberculosis.

The administration and results (negative or if + mm induration) of the PPD skin test will be presented in subject data listing. The administration and results (value and positive or negative) of the QuantiFERON assay will be presented in subject data listing.

13.3.2.5 Chest X-ray

A chest X-ray (postanterior and lateral view) will be performed at screening, unless available from a recent (within 12 weeks) X-ray. All chest X-ray results, including the X-ray date, will be presented in a subject data listing.

13.3.2.6 Prior and Concomitant Medications

Medications taken 60 days before the Screening Visit and up to the Safety Follow-up Visit will be summarized by preferred term using the World Health Organization-Drug Dictionary (WHO-DD) for the FAS set as frequency tables in 2 parts:

Prior medication: medication that started before the first dose of study drug, regardless of when dosing of the medication ended.

Concomitant medication: medication received at or after the first dose of study drug, or medication that was received before initial dosing and continued after initial dosing of study drug, or with missing stop date.

Medication that started before the first dose of study drug and continued after the first dose of study drug will be summarized as prior medication and separately as concomitant medication. Medications with a missing start date will be considered to have a start date before the first dose of study drug.

Concomitant medication as defined above will also be summarized by preferred term using the World Health Organization-Drug Dictionary (WHO-DD) for the FAS set using Anatomical Therapeutic Chemical (ATC) level 1 and level 2 coding. In some drug categories, additional lower level ATC coding will also be displayed (NSAIDs, systemic corticosteroids, DMARDs, proton pump inhibitors, anti-infective agents, narcotic analgesics).

13.3.2.7 Study Drug Exposure

Exposure to study drug (i.e., duration of treatment) will be summarized in terms of the duration of subject treatment (in days). Duration of treatment (computed as date of the last dose of study drug minus date of the first dose of study drug plus 1) will be summarized using descriptive statistics. Study drug exposure with the relevant information will be presented in an individual subject data listing for all enrolled subjects.

Exposure summaries will be based on the Safety set.

13.3.2.8 Study Drug Compliance

The number of tablets planned is calculated based on the treatment duration for each visit interval. Compliance based on the study medication pill counts will be presented in a listing for the Safety Set. Compliance summaries will be tabulated.

13.3.2.9 Baseline Hand and Foot X-RAY

The central reading facility (single reader) will read hand and foot X-rays for the baseline vdHmTSS. The vdHmTSS score will be divided by the calculated duration of RA (in years) at study entry, to estimate the annual progression rate for erosions in each subject before study participation. The definition of no erosions at baseline will be an average vdHmTSS erosion subscore <1.

13.3.3 Efficacy Analysis

The primary efficacy analysis will assess the clinical response to 3 dose regimens of VX-509 administered comparing to placebo at Week 12 in subjects with active RA on stable DMARD therapy. All efficacy analyses will utilize the FAS or MRI Set or Synovial biopsy Subset, as applicable.

13.3.3.1 Analysis of Primary Variables

Clinical response will be measured by: proportion of subjects who achieve an ACR20-CRP response at Week 12, change from baseline in the DAS28-4(CRP) score at Week 12 and change from baseline of RAMIS scores. ACR responses for primary and secondary efficacy will be calculated using nonresponder imputation, where missing responses for any reason will be considered nonresponders.

13.3.3.1.1 **ACR20-CRP Response**

The response rate of ACR20-CRP at Week 12 will be summarized by the randomized treatment group and 95% confidence interval (CI) for each treatment group comparing to placebo will use the M&N method, a score-based interval. ⁵¹ Cochran-Armitage trend test will be performed at Week 12.

